7.4.4. Adverse Events of Special Interest

The investigator or site staff will be responsible for detecting, documenting and reporting any event that may represent the AEs of special interest listed below (using preferred terms):

- Thrombosis and/or tissue ischemia secondary to excessive erythropoiesis

- Death, myocardial infarction, stroke, heart failure, , thromboembolic events, thrombosis of vascular access
- Cardiomyopathy
- Pulmonary artery hypertension
- Cancer-related mortality and tumor progression and recurrence
- Esophageal and gastric erosions
- Proliferative retinopathy, macular edema, choroidal neovascularization
- Exacerbation of rheumatoid arthritis

The results of any investigation should be recorded on the AE page and in the relevant AE of special interest page of the subjects' eCRFs.

7.4.5. Possible Suicidality Related Adverse Events

If during the study there is an occurrence of an AE or SAE which in the investigator's opinion, is possibly related to suicidality, the Possible Suicidality Related Adverse Events (PSRAE) eCRF form should be completed (in addition to the AE and SAE pages, as appropriate).

This event may include, but is not limited to, one that involves suicidal ideation, a preparatory act toward imminent suicidal behavior, a suicide attempt, or a completed suicide. The investigator will exercise his or her medical and scientific judgment in deciding whether an event is possibly related to suicidality.

7.4.6. Pregnancy

Details of all pregnancies in female subjects will be collected after the start of dosing and until 7 days after the last dose.

- If a pregnancy is reported, the investigator should inform PPD within 2 weeks of learning of the pregnancy and should follow the procedures outlined in [Appendix 9](#).

7.4.7. Height and Weight

Height and weight will be measured as specified in the Time and Events Table ([Table 6](#)). Weight will be measured in clinic with the subject wearing indoor daytime clothing with no shoes. For HD subjects, this will be measured pre and post dialysis when possible, or at study visits between dialysis sessions. For PD subjects these assessments will be done at study visits, as per standard of care.

Estimated dry (target) weight will be calculated at each study visit as specified in the Time and Events Table ([Table 6](#)).

7.4.8. Blood Pressure and Heart Rate

Measurement of systolic blood pressure (SBP), diastolic blood pressure (DBP) and heart rate (HR) will be taken at the time points specified in the Time and Events Table (Table 6).

- One measurement each of SBP, DBP and HR will be taken, except at Day 1, Week 52, and the Early Treatment Discontinuation visit (if applicable), when SBP, DBP and HR will be measured in triplicate.
- For HD subjects, measurements will be taken pre-and post dialysis with the subject in a semi-supine or seated position in the dialysis chair after at least a 5-minute rest period.
- For PD subjects, this assessment will be done at study visits, as per standard of care.

SBP, DBP, and HR will be performed before collection of blood samples for laboratory testing, where applicable.

7.4.9. Electrocardiogram (ECG)

ECG measurements will be taken at the time points specified in Table 6 and must be recorded pre-dialysis. Full 12-lead ECGs will be recorded with the subject in a supine position. Heart rate, PR interval, QRS duration, and QT (uncorrected) interval will be measured. QTcB will be calculated (machine-read or manually).

For the Day 1 ECG, two additional ECGs are required if the initial ECG indicates prolonged QTc using the automated or manually calculated QTcB value. The average QTcB value of all three ECGs will be used to determine eligibility (Section 5.2 for detail). Additional details are provided in the SRM.

ECG data will be read locally by a physician with experience in reading and interpreting ECGs. The over-read of the Day 1 ECG is required to confirm eligibility. Additional details are provided in the SRM.

All ECGs will be performed before measurement of SBP, DBP, HR (in-center HD only) and before collection of blood samples for laboratory testing.

7.4.10. Ultrasound

An ultrasound of the kidneys and adrenal glands will be performed prior to randomization (Day 1). It is understood that the adrenal glands will not always be able to be visualized. Non-visualization of the adrenals is NOT a reason to exclude subjects from randomization. Further details are provided in the SRM.

A documented ultrasound of the kidneys within the 6 months prior to screening may be used to assess entry criteria (Section 5.2), provided the size and cyst category has been

reported. If a more sensitive imaging study (e.g., MRI, CT) has been performed within this timeframe and a report is available, this may be used in place of the ultrasound.

7.4.11. Clinical Laboratory Assessments

All protocol required laboratory assessments, as defined in [Table 8](#), must be conducted in accordance with the Laboratory Manual, and Protocol Time and Events Schedule ([Table 6](#)). Laboratory assessments will be done pre-dialysis for HD subjects and at the study visits for PD subjects, as per standard of care.

Laboratory requisition forms must be completed and samples must be clearly labeled with the subject number, protocol number, site/center number, and visit date. Details for the preparation and shipment of samples will be provided by the laboratory and are detailed in the SRM. Reference ranges for all safety parameters will be provided to the site by the laboratory responsible for the assessments.

If additional non-protocol specified laboratory assessments are performed at the institution's local laboratory and result in a change in subject management or are considered clinically significant by the investigator (e.g., SAE or AE or dose modification) the results must be recorded in the subject's source notes.

Refer to the SRM for appropriate processing and handling of samples.

All study-required laboratory assessments will be performed by a central laboratory with the exception of HemoCue Hgb which will be performed at the clinical site. The results of each HemoCue Hgb must be entered into the subject's eCRF.

Table 8 Protocol Required Laboratory Assessments

Laboratory Assessments	Parameters		
Hematology	Platelet count	RBC indices:	WBC count with Differential
	RBC count	MCV	Neutrophils
	Reticulocyte count	MCH	Lymphocytes
	Hgb	MCHC	Monocytes
	Hematocrit	RDW	Eosinophils Basophils
Clinical Chemistry¹	ALT	AST	Bilirubin (total and direct/indirect)
	Potassium (serum)	Urea (serum)	Albumin (serum)
	Calcium (total and albumin-adjusted)	Inorganic phosphate	Creatinine (eGFR CKD-EPI) ^{4,5}
Iron parameters	Serum iron	Ferritin	UIBC
	Hepcidin	TSAT (calculated)	TIBC (calculated)
Lipid parameters	Total cholesterol	LDL-C (direct)	HDL-C
Other laboratory tests	Serum hCG pregnancy test ²	Follicle stimulating hormone ³	Estradiol ³
	HemoCue Hgb	hsCRP	iPTH
	Stored sample (blood)	Vitamin B12	Folate

Abbreviations: WBC, white blood cells; MCV, mean corpuscular volume; MCH, mean corpuscular hemoglobin; MCHC, mean corpuscular hemoglobin concentration; RDW, red blood cell distribution width, AST, aspartate transaminase; ALT, alanine transaminase; LDL-C, low density lipoprotein-C; HDL-c high density lipoprotein-C; UIBC, unsaturated iron binding capacity; TIBC, Total iron binding capacity; TSAT, Transferrin saturation; hsCRP, high-sensitivity C-reactive protein; iPTH, intact parathyroid hormone; hCG, human chorionic gonadotropin; CKD-EPI, Chronic Kidney Disease Epidemiology Collaboration

1. Details of Liver Chemistry Stopping Criteria and Required Actions and Follow-Up Assessments after liver stopping or monitoring event are given in [Appendix 6](#).
2. For females of reproductive potential only.
3. Screening only. As needed in postmenopausal women where their menopausal status is in doubt (see Inclusion Criteria Section [5.1](#))
4. Detail on the regional specific calculation will be summarized in the SPM.
5. Creatinine and eGFR will only be tested and calculated at screening and randomization

[figure not shown]
All laboratory tests with values that are considered clinically significantly abnormal during participation in the study or within 7 days after the last dose of randomized treatment should be repeated until the values return to normal or baseline. If such values do not return to normal within a period judged reasonable by the investigator, the etiology should be identified and the Sponsor should be notified.

7.4.12. Liver Chemistry Stopping Criteria

Liver chemistry stopping and increased monitoring criteria have been designed to assure subject safety and evaluate liver event etiology (in alignment with the FDA premarketing clinical liver safety guidance).

[figure not shown]
<http://www.fda.gov/downloads/Drugs/GuidanceComplianceRegulatoryInformation/Guidances/UCM174090.pdf>

Phase 3 Liver Chemistry Stopping and Increased Monitoring Algorithm

Liver Safety Required Actions and Follow up Assessments Section can be found in [Appendix 6](#).

Phase 3-4 Liver Chemistry Increased Monitoring Algorithm with Continued Therapy for ALT $\geq 3 \times \text{ULN}$ but < $8 \times \text{ULN}$

Liver Safety Required Actions and Follow up Assessments Section can be found in [Appendix 6](#).

7.4.12.1. Randomized Treatment Restart

If a subject meets liver chemistry stopping criteria, do not restart randomized treatment unless there is a clear underlying cause for the liver stopping event other than drug-induced liver injury and:

- GSK Medical Governance approval **is granted in writing**
- Ethics and/or IRB approval is obtained, if required, and
- Separate consent for treatment restart is signed by the subject

The full liver safety drug restart guideline is provided in [Appendix 6](#).

7.5. Pharmacokinetics (PK)

PK sampling will be performed in all in-center HD subjects randomized to the daprodustat arm.

Blood samples will be collected at the Week 4, Week 8 **or** Week 12 visit (i.e., PK is collected at one visit only, based on convenience for the subject/site). Samples will be collected at the following times relative to dosing of randomized treatment:

- Predose, 0.5, 1, 2, and 3 h post dose.

On the day of the scheduled PK visit:

- The subject is to be instructed **not** to take their dose at home before the visit, but to take the dose in the clinic after the pre-dose sample is collected.
- The dose taken in the clinic should be from the same bottle(s) the subject has been using prior to the PK visit, **not** from any newly dispensed bottle(s) at the PK visit. [Note: a subject placed on a dose hold at the previous visit should not have PK samples taken; PK collection should be delayed until the visit after the subject has restarted study treatment.]
- Record the date and actual time of the dose taken in the clinic and three doses prior to the visit, and the date and actual time of all PK samples collected. Samples may be collected within ± 20 min of the planned collected time.
- Based on the time of dosing, samples may be obtained before, during, or after any dialysis procedure. The start and stop time of the dialysis procedure will also be recorded at this visit.

Plasma PK analysis will be performed under the control of GSK PTS-DMPK/Scinovo, the details of which will be included in the SRM. Concentrations of parent daprodustat

and metabolites (GSK2391220 (M2), GSK2531403 (M3), and GSK2531401 (M13)) will be determined in plasma samples using the currently approved bioanalytical methodology. Raw data will be archived at the bioanalytical site.

7.6. Genetics

Information regarding genetic research is included in [Appendix 10](#). Samples for genetic analysis will be taken at the time points specified in the Time and Events Table ([Table 6](#)).

7.7. Patient Reported Outcomes

The patient-reported effect of daprodustat and rhEPO on symptoms, health-related quality of life (HR-QoL), and health status (e.g. utility) will be assessed. Symptoms will be assessed using a symptoms questionnaire which is specific to anemia of CKD (CKD-AQ). Overall symptom severity will be assessed using the patient global impression of severity (PGI-S) and overall symptom change using the patient global impression of change (PGI-C). Quality of life will be measured via SF-36, and health status via the EQ-5D-5L and EQ-5D-VAS. In addition, healthcare resource utilization will be assessed including out-patient visits.

All questionnaires used in this study have been translated and culturally adapted use in local country languages and will be administered electronically only. Specific instructions on how the subject is to complete the scales and the process for data entry is provided in the SRM. Details on patient reported outcomes are provided in the study reference manual.

The CKD-AQ, PGI-S, PGI-C, HR-QoL, and Health Status questionnaires should be completed by subjects at a clinic visit, in the order specified: PGI-S, PGI-C, CKD-AQ, SF-36, EQ-5D 5L, and EQ-VAS. Subjects who are unable to or require assistance to read must not complete the questionnaires. If there are other exceptional circumstances whereby the Patient Reported Outcomes assessments cannot be conducted, the completion of these assessments will be discussed with the Sponsor on a case-by-case basis.

7.7.1. Chronic Kidney Disease - Anemia Questionnaire (CKD-AQ)

A novel symptom questionnaire – CKD-AQ has been developed to collect concepts of interest for the anemia of CKD population over the past 24 hours. Unlike the Functional Assessment of Cancer Therapy – Anemia (FACT-AN) and Functional Assessment of Chronic Illness Therapy – Fatigue (FACIT-Fatigue) which have not demonstrated content validity specific for the anemia of CKD population, the novel CKD-AQ instrument was developed to verify and ensure that concepts specific for anemia of CKD were captured and measured. It will measure both the frequency and/or severity in anemia of CKD concepts such as weakness, energy, tiredness, shortness of breath, exertion, chest pain, memory, concentration, standing, sleep and distress over the past seven days.

7.7.2. Patient Global Impression of Severity (PGI-S) and Patient Global Impression of Change (PGI-C)

The Patient Global Impression of Severity (PGI-S) is a 1-item questionnaire designed to assess patient's impression of disease severity of their anemia of CKD. It is measured on a 5-point disease severity scale (absent, mild, moderate, severe, or very severe) during the past 24 hours.

The Patient Global Impression of Change (PGI-C) is a 1-item questionnaire designed to assess a subject's impression of symptom change of their anemia of CKD. It is measured on a 7-point Likert-type response scale (very much improved, moderately improved, minimally improved, no change, minimally worse, moderately worse, or very much worse) since they first started the study.

7.7.3. Health Related Quality of Life (SF-36)

The SF-36 acute version is a general health status questionnaire designed to elucidate the subject's perception of their health on several domains, including physical functioning, role physical, bodily pain, vitality, social functioning, role emotional, mental health, and general health. The questionnaire contains 36 questions within these domains that ask the subject to recall how they felt during the past seven days.

7.7.4. Health Status (EQ-5D-5L & EQ-VAS)

EQ-5D-5L consists of two concepts – the EQ-5D-5L descriptive system and the EQ-VAS. The EQ-5D-5L is a self-reported descriptive system of health-related quality of life states consisting of five dimensions (mobility, self-care, usual activities, pain/discomfort, anxiety/depression) each of which can take one of five responses. The responses record five levels of severity (no problems/slight problems/moderate problems/severe problems/extreme problems) within a particular EQ-5D dimension. Self-reported health status captured by EQ-5D-5L relates to the subject's situation at the time of completion. The EQ VAS records the respondent's self-rated health on a vertical, visual analogue scale where the endpoints are labeled 'the best health you can imagine' and 'the worst health you can imagine'. This information is used as a quantitative measure of health outcome as judged by individual subjects.

7.7.5. Psychometric Analyses of the CKD Anemia Symptoms Questionnaire (CKD-AQ)

In order to establish and evaluate the measurement properties of the CKD-AQ, an interim cut of blinded observations of the first 50 subjects who completed the week 28 visit will be taken. In order to establish content validity, the data cut will require a comparison to the following variables: PGI-C, PGI-S, Hgb, SF-36, demographic & baseline clinical characteristics. All data will be abstracted from screening until week 28.

The interim data cut will be used to conduct confirmatory factor analysis in order to establish a scoring algorithm for potential instrument domains and to evaluate the reliability, validity and responsiveness of the instrument without regard to treatment group. A full description of the data cut, variables of interest and analyses to establish

the scoring and evaluate the measurement properties of the CKD-AQ will be specified *a priori* within the psychometric analysis plan.

7.8. Storage Biomarkers

Blood (serum and plasma) samples will be collected as outlined in the Time and Events Table (Table 6) for potential future analysis of CV risk and iron metabolism.

8. DATA MANAGEMENT

- For this study, subject data will be entered into eCRFs, transmitted electronically and combined with data provided from other sources in a validated data system.
- Management of clinical data will be performed in accordance with applicable GSK standards and data cleaning procedures to ensure the integrity of the data, e.g., removing errors and inconsistencies in the data.
- Adverse events and concomitant medications terms will be coded using MedDRA (Medical Dictionary for Regulatory Activities) and an internal validated medication dictionary, GSKDrug, respectively.
- eCRFs (including queries and audit trails) will be retained by GSK, and copies will be sent to the investigator to maintain as the investigator copy. Subject initials will not be collected or transmitted to GSK according to GSK policy.

9. STATISTICAL CONSIDERATIONS AND DATA ANALYSES

9.1. Primary Hypotheses

The primary Hgb efficacy objective will assess the estimand defined as the comparative treatment effect in mean Hgb change between baseline and EP (i.e., Weeks 28 to 52 inclusive) in all randomized subjects; defined as those who remain in follow-up throughout the period of stabilization and have at least one Hgb assessment during the EP (i.e., Weeks 28 to 52) regardless of adherence to study treatment. The analysis will test whether daprodustat is non-inferior to rhEPO according to the following statistical hypotheses:

- **Null:** The difference in mean change in Hgb between baseline and EP, between treatment arms (daprodustat-rhEPO), is less than or equal to -0.75 g/dL.
- **Alternative:** The difference in mean change in Hgb between baseline and EP, between treatment arms (daprodustat-rhEPO), is greater than -0.75 g/dL

The non-inferiority margin is pre-defined as -0.75 g/dL; selected to be consistent across all clinical trials in the daprodustat Phase 3 clinical development program in subjects with anemia of chronic kidney disease, and determined based upon a combination of clinical judgment, statistical reasoning and regulatory guidance for designing non-inferiority trials.

Statistical significance of non-inferiority will be assessed at the one-sided 2.5% level. An analysis of covariance (ANCOVA) model including randomization stratification factors, baseline hemoglobin and treatment will be used to obtain a point estimate and the two-sided 95% CI for the treatment difference (daprodustat-rhEPO) and generate the p-value for the non-inferiority test. The non-inferiority p-value will show strength of evidence against the null hypothesis. Non-inferiority will be established if the lower limit of the two-sided 95% CI for the treatment difference is greater than -0.75 g/dL.

9.2. Sample Size Considerations

9.2.1. Sample Size Assumptions

The size of this study has been determined to be sufficient to meet the ICH E1 guideline for subject exposure, number and duration and to provide at least 90% power to test the primary non-inferiority hypothesis with a two-sided 95% CI.

Approximately 300 subjects are planned to be randomized (150 per arm) to receive daprodustat or rhEPO, to provide at least 100 subjects exposed to daprodustat for one year. Subjects will be treated to achieve and maintain Hgb between 10 and 11 g/dL. The expected difference in mean Hgb change from baseline and the EP, between arms, is 0 g/dL and the anticipated between subject standard deviation (SD) is 1.5 g/dL, based on historical rhEPO trials and daprodustat clinical trial experience to date. With a pre-specified non-inferiority margin of -0.75 g/dL, a two-sample T-test and assuming that up to approximately 30% of subjects will permanently stop randomized treatment before Week 28 (start of EP), 300 randomized subjects will provide >90% power to test the primary hypothesis.

With 300 randomized subjects, it is anticipated that the difference in mean Hgb change from baseline between arms will be estimated with a precision of 0.408 g/dL (half width of the two-sided 95% CI) and the largest (most negative) difference between arms that would meet the statistical criterion for non-inferiority would be -0.342 g/dL.

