5.5. Permanent Discontinuation of Randomized Treatment

Every effort should be made to keep subjects in the study including those who permanently stop randomized treatment. A subject may permanently discontinue randomized treatment at any time at his/her own request, or at the discretion of the investigator for safety, or compliance reasons. A subject must permanently discontinue randomized treatment for the pre-specified reasons below:

- Kidney transplant
- Reaching criterion to receive rescue (Section [6.11](#))
- Becomes pregnant or intends to become pregnant during the study
- Liver chemistry abnormalities exceeding the threshold criteria (Section [7.4.12](#))
- Diagnosis of cancer (new or recurrent), with the exception of localized dermal squamous cell or basal cell carcinoma
- Need for more than 14 days use of a prohibited medication (Section [6.9.2](#))

In all cases, the reason for randomized treatment discontinuation and the date of the last dose will be recorded in the subject's electronic case report form (eCRF) and the subject will continue in the study as described in Section [5.5.1](#).

Subjects may be re-approached about restarting randomized treatment in certain circumstances if the Sponsor and the investigator agree.

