
Treatment Stop Date
 
 • Calculated as the latest randomized treatment dose stop date for subjects who have a non-missing treatment start date. Note that this date could come from a randomized treatment exposure record with a missing or partial dose stop date if the associated dose start date for that exposure record is on or after the last non-missing randomized treatment dose stop date. • The eCRF allows for the possibility of missing or partial dates to be recorded for the dose stop date on the study treatment form (i.e., missing day, or day and month, or day and month and year). In such a case, the following conventions will be applied in order to impute a treatment stop date: 
 ○ Missing day: 
 ▪ The last day of the month will be used, unless the study completion or withdrawal date also occurs in the same month; in the case, the study completion or withdrawal date will be used. ○ Missing day and month: 
 ▪ '31' will be used for the day and 'Dec' will be used for the month, unless the study completion or withdrawal date also occurs in the same year; in this case, the study completion or withdrawal date will be used. ○ Missing day, month and year: 
 ▪ The study completion or withdrawal date will be used only for subjects who have a non-missing treatment start date.

End of Treatment Value
 
 • Only defined for subjects with a non-missing treatment start date • Hgb, iron, transfusion and PRO parameters: the latest value on or before the treatment stop date + 1 day. • Blood pressure, central laboratory, and vital signs parameters: the latest value on or before the last non-zero dose date + 1 day.

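### Does losing up to 30% of subjects before Week 28 undercut the aim of at least 100 subjects on daprodustat for one year?

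*Protocol*

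**What the plan says.** Protocol 9.2.1 gives two reasons for the size of the study. The first is exposure: "The size of this study has been determined to be sufficient to meet the ICH E1 guideline for subject exposure, number and duration". The second is at least 90% power for the primary non-inferiority test. About 300 subjects, 150 per arm, are planned "to provide at least 100 subjects exposed to daprodustat for one year".

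The power statement that follows assumes that "up to approximately 30% of subjects will permanently stop randomized treatment before Week 28 (start of EP"). The paragraph after it says the difference between arms "will be estimated with a precision of 0.408 g/dL (half width of the two-sided 95% CI"). Protocol 9.2.2 tabulates power for 20% to 40% non-evaluable subjects, with n=105 per arm in the 30% column. Protocol 9.2.3 plans no sample size re-estimation. Neither document states a stopping rate for Weeks 28 to 52 or for the full 52 weeks.

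On stopping, Protocol 5.5 lists mandatory reasons: "A subject must permanently discontinue randomized treatment for the pre-specified reasons below". It also leaves a way back: "Subjects may be re-approached about restarting randomized treatment in certain circumstances if the Sponsor and the investigator agree". For liver events, Protocol 7.4.12.1 says "do not restart randomized treatment unless there is a clear underlying cause for the liver stopping event other than drug-induced liver injury", with further approvals and consent required. SAP 10.6.1 defines the treatment stop date as follows: "Calculated as the latest randomized treatment dose stop date for subjects who have a non-missing treatment start date".

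**The concern.** The exposure aim carries no retention condition, whereas the power claim beside it does. The printed precision shows that the sponsor worked with 105 subjects per arm, so it seems fair to hold the exposure count to the same case. From 105, only 5 subjects can be lost over 24 weeks, while the mandatory stopping reasons (among them transplant, rescue, liver criteria and cancer) continue to apply. At first sight this needs a steep fall in discontinuation that the protocol does not mention.

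At stake is whether a reader can check one of the two stated reasons for the sample size, and whether the study might fall short of its exposure aim with no mechanism to correct it.

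**Working it through.** **Inputs.** From Protocol 9.2.1: 150 per arm, a one-year exposure aim of 100, up to about 30% stopping before Week 28, SD 1.5 g/dL, margin -0.75 g/dL, expected difference 0. Treatment lasts 52 weeks (Protocol 4.1). Assumptions made here: all 150 start daprodustat, the 30% applies equally to both arms, one year means the 52-week treatment period, and restarts are ignored.

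**Reproducing the plan's own figures.**
- Subjects left at Week 28: 150 × 0.70 = 105, as printed in 9.2.2.
- Half-width: t(0.975, 208) × 1.5 × √(2/105) = 0.408, as printed. With n=120 it would be 0.381, and with n=150 it would be 0.341.
- Largest difference meeting the criterion: -0.75 + 0.408 = -0.342, as printed.
- Power at n=105 from the noncentral t distribution: 95.0%, against 95% in 9.2.2.

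The printed figures contain no arithmetic error.

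**What the exposure aim requires.** Total stops allowed by Week 52: 150 - 100 = 50, and 50/150 = 33.3%. The table splits this allowance by the share stopping before Week 28. The last column continues the same weekly stopping rate to Week 52, that is, 150 × (1 - d)^(52/28), where d is the share stopping before Week 28. This constant rate is an illustration and is not in the documents.

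| Stop before Week 28 | Left at Week 28 | Later stops allowed | Left at Week 52, constant rate |
|---|---|---|---|
| 10% | 135 | 35 (25.9%) | 123.3 |
| 15% | 127.5 | 27.5 (21.6%) | 110.9 |
| 20% | 120 | 20 (16.7%) | 99.1 |
| 25% | 112.5 (printed as 113) | 12.5 (11.1%) | 87.9 |
| 30% | 105 | 5 (4.8%) | 77.3 |

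**Break-even at a constant rate.** Solve (1 - d)^(52/28) = 100/150. This gives 1 - d = (2/3)^(28/52) = 0.804, so d = 19.6%.

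**Does the rate have to fall?**
- At 30% early stopping: the weekly rate before Week 28 is -ln(0.70)/28 = 0.01274. The rate allowed afterwards is -ln(100/105)/24 = 0.00203. The ratio is 0.16, a steep fall.
- At 20% early stopping: -ln(0.80)/28 = 0.0080 before, and -ln(100/120)/24 = 0.0076 allowed after. The ratio is 0.95, almost no fall.

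The steep fall is therefore a feature of the upper bound and does not hold across the stated range.

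**The case for a change.** The strongest argument for acting is that 30% is the sponsor's working case. The half-width of 0.408 arises only at n=105, so the protocol quotes both power and precision there. In that case the margin is thin. If 5% of the 105 stopped later, 99.8 would be expected at Week 52, with a 57% chance of reaching 100; at 10%, 94.5 would be expected and the chance is 4%. These later rates are assumptions. Protocol 9.2.2 varies power only and never tests exposure.

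The arithmetic stands, and so does the observation that no later rate is given. It does not follow that 30% was the loss expected when the exposure count was set. The text gives it as a maximum, inside the power sentence. It is also a cautious choice for power: Protocol 9.4.1 uses hemoglobin values regardless of adherence, so a subject who stops treatment need not be lost to the primary analysis. Quoting precision at the same bound is consistent with that caution.

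A second argument is that the exposure categories in SAP 6.2.6 break at 12 months, so a subject dosed exactly to Week 52 falls in the same category as one who stopped in month 7. That is true of the category table, but the information is not lost. SAP 6.2.2 reports by arm how many subjects did not stop treatment early and plots time to discontinuation, and SAP 6.2.6 lists dose start and stop dates.

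Restarts work in the plan's favour. Because the stop date is the latest one, a subject who restarts accrues exposure through the gap. The number is not given and is left out of the counts above.

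**Conclusion.** The exposure aim depends on a retention assumption that the protocol does not write down, but the documents do not contradict it. It is attainable within the stated range: at most 50 of 150 may stop by Week 52, and early stopping of about 19.6% reaches 100 without any slowing. It becomes tight only towards the 30% ceiling, where 5 later stops are allowed.

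This is missing detail, and supplying it gains nothing for the trial. The sample size, power of 95%, half-width of 0.408 and all analyses would stay the same. No test or decision rule uses the exposure count, and the achieved exposure will be reported by arm whatever was assumed. A protocol amendment to record a subtraction that a reader can do from 9.2.1 and 9.2.2 would be out of proportion.

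The conclusion rests on all 150 starting daprodustat, equal stopping in both arms and one year meaning the 52-week treatment period. It takes the protocol's own count of 100 as the yardstick, because the guideline it cites is not quoted.
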